Urine and/or oral saliva specimens will be collected/tested at baseline using commercially-available drug test kits and specimen containers. We will also collect and test urine and/or oral saliva at the time of the follow-up EEG assessment. In addition, urine specimens may also be collected and tested using commercially-available drug test kits at check-in appointments if the participant is not actively involved in CM and/or has missed recent CM visits. However, it is noted that collection of such supplemental urine specimens at check-in timepoints would not apply if (1) lab-based urinalysis for substance use has recently been completed for clinical or research purposes, (2) the participant refuses, or (3) the participant is not available or able to provide a specimen. All urine and oral saliva specimens collected for testing with commercially-available drug test kits in the context of these described research activities will be marked with indirect identifiers only and will be disposed of immediately after testing.

Samples Collected in the Context of Treatment (CM; *Direct Identifiers*):

During the 12 week treatment interval, patients will be subject to routine urinalysis (twice weekly). Urine specimens will be collected (and may be witnessed, if necessary) by nursing staff at the Center for Treatment of Addictive Disorders (CTAD) or research staff at the Research Office Building and tested for cocaine (and possibly other substances) by the CM therapist using a point-of-care diptest in order to provide the patient with immediate results for the purpose of determining CM prize draws. Confirmatory urinalysis will subsequently be conducted to verify point-of-care results. Urine specimens will therefore be forwarded to VAPHS laboratory staff for processing. For this reason, urine specimens collected in the routine clinical course of CM will be marked with direct identifiers prior to submission to the lab. However, it is noted that all urine collection/testing procedures to be conducted within the context of CM parallel those already used in routine clinical (i.e., non-research) administration of CM and other substance use treatment programming at VAPHS. It is additionally noted that participants may always decline to provide observed urines for lab-based processing and may alternately elect to provide urine specimens (not marked with direct identifiers) for kit-based testing by research personnel, as described above.

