
Risks and Benefits: With respect to Substudy 1, participants will have the opportunity to receive a telemedicine version of CM that is not otherwise available at our site and this may benefit Veterans for whom remote treatment options are indicated or preferred. There are no significant risks associated with the proposed telehealth-based protocol - rather, it is expected that this CM option may be lower risk for some Veterans. This substudy will combine the use of an approved "standard of care" treatment option with approved VA telehealth technology (e.g., VVC) and so does not significantly deviate from standard clinical practice. However, due to the use of Veteran-administered oral fluid testing, this treatment protocol would currently only be permissible in the context of research. Participants will be informed of confidentiality and privacy considerations that are unique to telehealth at the start of each session (for example, ensuring that the Veteran has sufficient privacy in their current environment), as is typical of all such clinical interactions.

SUB-STUDY 2: REMOTE PHYSIOLOGICAL MONITORING FOR STATE-DEPENDENT PREDICTORS OF CRAVING AND USE

SUB-STUDY 2 Specific Aim: Establish feasibility of data collection using wearable sensors and identify promising physiological markers of stimulant craving and/or use between treatment encounters.

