In this sub-study, I will leverage the existing infrastructure of my CDA research to collect supplemental physiological and activity data via wearable sensors to identify potential real time markers of craving and use. Participants will be recruited through our established recruitment pipeline. Following enrollment in the parent protocol, up to 45 participants will be invited to participate in additional physiological and activity monitoring during the first two weeks of the 12-week treatment interval. Individuals who decline to participate will be asked to share specific concerns contributing to this decision. Those who choose to enroll will be outfitted with a wrist-worn ActiGraph wGT3X-BT wearable activity monitor and Bluetooth-enabled Polar H7 Heart Rate monitor. Together, these medical-grade wearable devices enable high resolution monitoring of heart rate (including R-R intervals), physical activity (including sleep/wake time and related metrics), and compliance without conveying feedback to the wearer. Participants will receive training on routine maintenance of wearable devices, including requirements for recharging/changing batteries. Feedback regarding acceptability of wearable monitoring, as well as problems encountered, will be recorded at the beginning and end of sub-study participation. Devices will be returned at the conclusion of the 2-week recording period, whereupon data will be downloaded and the participant will be compensated \$40. Participants may additionally receive daily reminder calls during the 2-week recording interval to ensure that they are wearing the devices properly and to troubleshoot any problems that may arise. Upon request, participants may receive a copy of a clinical report, generated by ActiLife software, summarizing activity and sleep data from the recording interval.

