Data Analytic Plan. The number of participants declining to participate in the sub-study, as well as feedback regarding acceptability of wearable device monitoring will be quantitatively and qualitatively summarized. Data collected through ActiGraph/Polar wearable devices will be reviewed, preprocessed, and analyzed using ActiLife software. The proportion of data rejected due to noncompliance (detected using ActiLife's Wear Time Validation Tool) or poor electrocardiography (ECG) signal quality (determined through visual inspection) will subsequently be computed. Valid data segments will be subject to additional analyses investigating potential markers of high-risk states in wearable data streams. Based on previous work and known cardiovascular effects of stimulants, periods of elevated resting heart rate

are expected to predict self-reported stimulant use and subsequent stimulant-positive urinalysis. For example, periods of elevated heart rate associated with cocaine craving can be distinguished from use events based on duration (30-40 minutes for craving versus 2 hours for use). The number and duration of elevated resting heart rate intervals will be investigated as potential predictors of self-reported and objectively verified stimulant use using a mixed effects logistic regression approach. Additional exploratory features extracted from ECG and activity data (e.g., heart rate variability (linked to craving in alcohol users), sleep efficiency (known to be impaired during early cocaine abstinence), and number/duration of physical activity bouts) may also be considered. These preliminary analyses will serve to identify promising state-dependent markers from wearable data streams for future investigation. Importantly, a mobile interface to be developed under a separate protocol (Pro3566) will support ecological momentary assessment of craving, stress, and substance use and these data will critically inform future efforts to distinguish physiological markers associated with high-risk for use – of relevance to delivery of in the moment interventions – from actual use events.

View: 6 Study Population Summary

Study Population Summary

1.0 * What is the maximum number of subjects you plan to enroll at VAPHS?

215 (Target Sample Size Primary Study = 140; an additional 1-5 Veterans may be invited to participate in Sub-Study 1)

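### Sub-Study 2 looks for state-dependent heart-rate markers, but its stated model does not separate within-person from between-person association, so a stable difference between people can look like a state marker

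*Combined protocol and SAP*

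**What the plan says.** Section 5.1 titles Sub-Study 2 "REMOTE PHYSIOLOGICAL MONITORING FOR STATE-DEPENDENT PREDICTORS OF CRAVING AND USE" and describes its purpose as "to identify potential real time markers of craving and use". On size and duration: "up to 45 participants will be invited to participate in additional physiological and activity monitoring during the first two weeks" (weeks counted from the start of treatment).

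The main inferential plan is one sentence in the Data Analytic Plan: "The number and duration of elevated resting heart rate intervals will be investigated as potential predictors of self-reported and objectively verified stimulant use". The only method that sentence names is mixed effects logistic regression. Heart rate variability, sleep and activity features may be added. The section closes: "These preliminary analyses will serve to identify promising state-dependent markers from wearable data streams for future investigation".

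The plan does not give the random-effects structure, covariates, centring, the definition of an elevated rate, the time unit linking intervals to outcomes, or an adjustment for unequal wear time. It states no alpha, power or effect size.

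**The concern.** A state-dependent marker tells you when a given person is at risk. That is a within-person question. A model with one slope per feature also uses the comparison between people: those who have more elevated intervals throughout may also be those who use more. A random intercept does not take this out, because the model assumes that the intercept is uncorrelated with the predictor.

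The protocol gives reasons to doubt that assumption. Participants are aged 18 to 75 with mild, moderate or severe cocaine use disorder (section 6.1). They continue any pharmacotherapy, some are in medication-assisted treatment, and nicotine dependence is measured (section 4). Stable differences of this kind could plausibly relate to both heart rate and use. If they do, a between-person difference could be carried into later work as a state signal.

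**Working it through.** **Model.** Let x be the interval count (or duration) for person i in period t, and m the person's mean over the monitored period. The separated model is

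logit P(use) = a + bW·(x − m) + bB·m + u,

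with u the random intercept. Entering x alone forces bW = bB, so the one slope estimates a weighted mixture. Its null hypothesis is that neither association exists.

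**Inputs from the documents.**
- At most 45 people, monitored for 2 weeks (section 5.1).
- Urine: "patients will be subject to routine urinalysis (twice weekly" (section 3.5), so 2 × 2 = 4 results per person.
- Timeline follow-back about weekly (section 4), taken here to yield up to 2 × 7 = 14 daily values.
- Two-sided 0.05 is assumed. The figure appears in the main-study power text; Sub-Study 2 states none.

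There is no figure in the plan to reproduce, so the effect has to be simulated. All other inputs are assumptions.

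**Simulation A** (45 people; random-intercept logistic model by 15-point quadrature; likelihood-ratio test; person SD 1.5 on the logit; 50-70% of predictor variance between persons; no within-person effect; 400 data sets per cell). Rejection rates for the undivided slope:

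| Outcomes per person | Person-level correlation with use 0.3 | 0.5 |
|---|---|---|
| 14 daily | 11-16% | 20-36% |
| 4 urine | 15-18% | 32-46% |

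With correlation 0 the undivided slope rejects in 4-7%. The deviation term rejects in 3-6% throughout. A further run at correlation 0.5 gave about 23-53% undivided and 3-8% split. Together the undivided range is roughly 11-50%.

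**Simulation B** (count predictor, mean 1.5 intervals per period; use in about 20% of periods; residual random-intercept SD 0.7; a trait shifting log interval rate by 0.3, 0.5 or 0.8 per SD and log-odds of use by 0, 0.5 or 1 per SD; Wald test; 600 data sets per cell, so Monte Carlo error is at most √(0.25/600) = 2.0 points). With no within-person effect:
- 45 people, trait linked to use: undivided 13-69% (14 outcomes) and 18-77% (4 outcomes).
- 20 people, trait linked to use: undivided 9-43%.
- No trait-use link: undivided 3-6%.
- Deviation term, all cells: 3.5-6.0%.

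**Middle case of B** (45 people, trait 0.5 on log rate and 1.0 on log-odds, true within-person odds ratio 1.00). Median slopes:

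| Outcomes | Undivided | Deviation | Person mean | Implied weight on between-person part |
|---|---|---|---|---|
| 14 | 0.122 (OR 1.13) | 0.005 | 0.892 | (0.122 − 0.005)/(0.892 − 0.005) = 0.13 |
| 4 | 0.236 (OR 1.27) | 0.007 | 0.674 | (0.236 − 0.007)/(0.674 − 0.007) = 0.34 |

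The blend is worse with fewer outcomes per person, so it bears most on the urine results.

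**Power of the split.** At log odds ratio 0.5 with 45 people and 14 records, if the person mean has no effect, the deviation term has 92% power against 87% undivided. If within and between effects are equal, the order reverses (two runs, ranges shown):

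| Outcomes, variance between persons | Deviation term | Undivided |
|---|---|---|
| 14, 50% | 92-93% | 95-96% |
| 14, 70% | 70-71% | 85-87% |
| 4, 50% | 31-38% | 49% |
| 4, 70% | 16-24% | 42-53% |

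In simulation B, a true within-person log-odds of 0.30 per interval is detected by the deviation term in about 98% of data sets with 14 outcomes and 47% with 4.

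**The case against.** The strongest reply has four parts.

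- **The plan is silent on how the counts are entered.** A reader might infer that the plan specifies raw, uncentred counts. It does not. It names features and a model class only. 'Elevated' could also be defined against each person's own baseline. That would reduce the problem, but people would still differ in the number and duration of their intervals.
- **The work is preliminary.** A reader might infer that the result directly selects markers for in-the-moment intervention. The plan leaves that to future efforts informed by momentary-assessment data under a separate protocol. It contains no 5% decision rule, so the rejection rates above measure a conventional claim, not a stated one. This limits the priority. It does not answer the point, because the stated output is still a list of state-dependent markers.
- **The sizes are assumed.** This stands. No correlation or variance share is given, 45 is a ceiling, and with no trait-use link the error is nominal. A reader might also infer that true markers would be masked by a trait of opposite sign. That can be simulated, but nothing in the documents suggests such a trait.
- **The split costs power.** This also stands. The plan's own rationale is that use raises heart rate for about 2 hours, so frequent users would accumulate more elevated intervals through the state mechanism itself. Within and between effects would then agree, and the undivided slope has more power. That extra power comes from comparing people, though, and such a comparison cannot by itself support a state-dependent claim.

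**Conclusion.** The point holds as a gap between target and model. As written, nothing separates within-person from between-person association, so a stable difference related to both interval frequency and use can appear as a state-dependent marker. It need not do so, and the documents do not show that such a difference exists.

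Under simulation A's assumptions the false-positive rate for a within-person claim is roughly 11-50%. Simulation B's wider assumptions give 9-77%. Without the correlation both stay near 5%. The mechanism does not depend on the exact inputs, but the rates do.

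Priority is low: the sub-study is optional, small and hypothesis-generating. A reader might infer that the trial's main results are affected; this analysis plays no part in Aims 1 or 2.

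**What to change.** In the Sub-Study 2 Data Analytic Plan:

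1. Enter each heart-rate feature as the person's mean over the monitored period plus the deviation from that mean, both in the mixed logistic model. Do the same for heart rate variability, sleep and activity features.
2. Base any state-dependent claim on the deviation coefficient. Report the person-mean coefficient separately as a between-person association.
3. Define 'elevated', the time window linking intervals to each outcome, and the adjustment for wear time.
4. State that with about 4 urine results per person the within-person test is low-powered, and present that result accordingly.

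The cost is one derived variable and one coefficient per feature, with no new data. The price is the loss of power shown above when within and between effects agree. It is largest for the urine outcome.

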*** Do you plan on enrolling patients into different categories:**

Yes **No**

If yes, please explain:

Participants who complete Screening and Baseline testing procedures will be randomized into two different conditions: VoucherPBCM (n = 70) or TangiblePBCM (n = 70. Details of the two study conditions are provided under Section 4. Healthy controls will either have no history of substance use treatment or will be considered to be in long-term recovery (i.e., having achieved > 1 year of abstinence from cocaine and other illicit substances). We will make an effort to match healthy controls to the patient sample based on age, sex, and smoking (nicotine use) status.

3.0 If this is a multi-site study, indicate the projected total subject accrual:

No.

4.0

*** Please provide a justification for the sample size:**

Power Analysis and Sample Size. In analyses of baseline predictors of treatment response in CM recipients (estimated n = 119-140) and long-term (i.e., six month) outcomes (estimated n = 105-140),

using the statistical rule of thumb of needing 10 observation per predictor, there will be adequate power to include 10-14 variables in regression-based analyses. Random Forest methods are further supported for an expanded set of variables, as this highly flexible and powerful approach has been validated in “wide datasets,” wherein the number of predictors exceeds the number of observations. With the anticipated enrollment of 140 participants, there will additionally be adequate power ($\beta = 0.20$, alpha = 0.05) to detect an effect size of $f = 0.12$ for the treatment adherence (adherent, non-adherent) X time (baseline, follow-up) interaction, supporting planned comparison of treatment-related change in neural and cognitive-behavioral measures between PBCM adherent and non-adherent subgroups. Assuming 15% attrition, the estimate of the detectable effect size for the treatment X time interaction for a total sample size of 119 is $f = 0.13$. The anticipated effect size of treatment-related change in synchronization likelihood between ACC-IPFC electrode sites is not known. However, previous work has established a medium-to-large effect size for treatment-related change in the ERN and N2 (in association with cognitive training) [69,70]. We have also proposed to compare the treatment-seeking CUD sample to the approximately 45 healthy controls who may be invited to participate in a comparison sample. Data from controls would help determine how CM-referred veterans differ from healthy individuals with respect to approaches to rewarding abstinence. However, it was ultimately not possible to enroll a sufficient healthy comparison sample at our site. In addition, due to factors that negatively impacted participant accrual over the course of the current study (as described elsewhere in the protocol) a revised analytic approach was developed to make use of a sample size that was significantly reduced relative to that originally projected.

An additional 1-15 Veterans will be invited to participate in Substudy 1, with the goal that at least one individual completes a full course of treatment via telehealth. This sample size is reasonable for a case study and also reflects financial considerations which may impact the ongoing availability of oral fluid testing supplies for this purpose.

View: 6.1 Study Population

Study Population

1.0

* Check all that apply to describe your study population:

Study Population

Non-Veterans

Special Populations X

Veterans X

Vulnerable populations X

Other

2.0 * Indicate the inclusion criteria for enrollment:

- Military Veterans, ages 18-75
- DSM-5 Criteria for Cocaine Use Disorder (Mild, Moderate, or Severe)
- Cocaine Use Within Past 45 Days (or past 60 days if in a controlled environment for part of this time)
- Stated Goal of Cocaine Abstinence or Reduced Cocaine Use
- Normal or Corrected-to-Normal Visual and Auditory Acuity (e.g., patients with glaucoma or tinnitus may be eligible)

These criteria will be assessed prior to enrollment and it is noted that many participants will no longer meet all the above-stated criteria throughout the full study interval. For example, time since most recent cocaine use may exceed 45-60 days in patients who achieve and maintain abstinence during Contingency Management treatment and this would not be considered grounds for withdrawal from the study.

Healthy controls will either have no history of substance use treatment or will be considered to be in long-term recovery (i.e., having achieved > 1 year of abstinence from cocaine and other illicit substances). We will make an effort to match healthy controls to the patient sample based on age, sex, and smoking (nicotine use) status.

For Sub-Study 1, 1-5 Veterans will be invited to take part in telehealth-based CM treatment sessions. We will specifically make an effort to invite individuals to participate for whom in-person CM sessions are not preferred because (1) the Veteran is at high risk for complications from COVID-19, (2) the Veteran is under quarantine due to COVID-positive status or housing-related restrictions, or (3) the Veteran has ongoing transportation problems that make attending in-person treatment sessions more difficult. All participants will be either be self-referred or clinician-referred to receive CM services and will meet general requirements for this type of treatment (e.g., ongoing problematic stimulant use). Participants must also be willing and able to participate in telehealth services, appropriate for telehealth care, and able to interact and communicate through audio and visual elements of the VVC platform. No exclusion criteria will apply. Participants in the substudy may be former (e.g., completed or withdrawn) participants from the primary protocol or participants determined ineligible to participate in the primary protocol.

3.0 * Indicate exclusion criteria for enrollment:

- History of Severe Traumatic Brain Injury, Seizure Disorder, or other Neurological Conditions resulting in structural and/or functional abnormalities of the brain that are expected to reduce interpretability of (or acquisition of generalizable knowledge from) psychophysiological datasets
- Severe or Unstable Medical or Psychiatric Condition that may interfere with study participation or the ability to follow the intervention protocol (e.g., suicidality, untreated secondary substance use disorder, ongoing cancer treatment, potential for future/frequent medical hospitalization)
- Pregnant or Lactating Women
- Moderate-to-Severe Neurocognitive Impairment per Medical Record or SLUMS ≤ 20 or Mini MoCA ≤ 10

- In Long-Term Residential Treatment In a Controlled Environment or Imminently Expected to Enter Such Treatment During the Study Interval at the time of Screening

These criteria will be assessed prior to enrollment and it is possible that participants will experience a change in one or more of these criteria over the course of the study. For example, patients may be admitted to residential treatment or experience a medical hospitalization (unrelated to participation) during the study interval. In an effort to collect full and complete longitudinal data on as many participants as possible, such circumstances will not necessarily result in participant withdrawal from the study. However, if any such change is determined to adversely impact the risk-to-benefit ratio of continued participation, investigator-initiated withdrawal of the participant will occur.

It is further noted that individuals living in transitional housing will be eligible for inclusion. In addition, patients who are scheduled to discharge from a residential treatment program (e.g. CTAD CORE) will be considered eligible if they are not imminently expected to seek admission to another residential treatment environment upon discharge.

Healthy controls will either have no history of substance use treatment or will be considered to be in long-term recovery (i.e., having achieved > 1 year of abstinence from cocaine and other illicit substances). Healthy controls will be excluded if they test positive for substance use (e.g., based on breathalyzer test results or urine drug testing) at the time of the baseline assessment. An effort will be made to achieve a healthy comparison sample that is demographically similar to the patient sample and it is noted that otherwise eligible individuals may be excluded in order to achieve this objective.

4.0 If there are any age, ethnic, language, or gender-based exclusion criteria, including the exclusion of any pregnant or lactating women, or those of child-bearing potential, please provide justification:

Pregnancy and/or lactation may alter event-related potentials under study herein. As it will not be possible to systematically evaluate the influence of pregnancy/lactation on event-related potentials in the current design, there is scientific justification for excluding these individuals.

5.0 Please specify why vulnerable subjects and/or special populations will not be enrolled:

6.0 With some exceptions as listed in VHA Handbook 1200.05, incompetent subjects cannot be enrolled in VAPHS approved research. Specify that you will not enroll incompetent subjects and the general rules to be used in making that determination:

We will not enroll incompetent subjects in the current protocol. Competence to provide informed consent will be evaluated during the informed consent process. Those who are unable to provide informed consent will be excluded from the study.

View: 6.2 Study Population- Vulnerable Populations

Study Population

1.0

* Check all that apply to describe your study population:

Children
Decisionally Impaired
Economically Disadvantaged X
Educationally Disadvantaged
Prisoners

2.0 * Describe the precautions, and any additional safeguards that will be taken to protect the rights and welfare of vulnerable subjects if they are to be enrolled. Also note that certain populations may feel pressured or be vulnerable to coercion or undue influence to participate in research. Indicate any special considerations that may be taken for such groups:

We will not specifically target economically disadvantaged individuals in our recruitment efforts. However, it is possible that Veterans interested in participation and eligible for the current study will be from economically disadvantaged backgrounds.

Several safeguards have been established to minimize the risk of coercion or undue influence and to protect the rights of our participants.

Some potential participants will be informed of the study by one of their providers. This will allow participants to discuss concerns regarding participation with someone who is not directly affiliated with the study and who is oriented toward the needs of the patient rather than the study. We believe this will prevent patients from feeling pressured to participate in the current study. We also expect that the majority of potential participants will self-initiate contact with study personnel directly. In these cases the potential participant has already decided that he/she is interested in the study, which may offset the risk of coercion.

While we will provide monetary compensation for time and travel, we believe that study payments are reasonable and would not be considered to be coercive. Participants will also be educated that "informed consent is an ongoing process" and that they can choose to stop participating at any time without financial penalty or loss of benefits to which the Veteran would otherwise be entitled. Before each procedure, a brief description will be provided, including the rationale for the procedure as well as what the participant can expect to experience. Participants will be provided with an opportunity to ask questions prior to each study procedure and will also be informed that they may decline to begin a procedure if they feel uncomfortable in any way. They will also be reminded throughout that they may choose to end participation at any time, even if this requires terminating a procedure that is already under way.

View: 6.2.3 Economically Disadvantaged

Economically Disadvantaged

1.0 * Target Number of Participants:

140

2.0 * Please provide a justification for including these subjects:

We will not specifically target economically disadvantaged individuals in our recruitment efforts. However, it is possible that individuals of low socioeconomic status will be identified as potential participants. Specifically, many patients with chronic substance use disorders are members of economically disadvantaged communities and substance use may also result in adverse consequences with respect to employment and income. Recruiting a representative sample of Veterans with substance use disorders is necessary to improve generalizability of the our findings and we would be unable to achieve a representative sample if we specifically excluded economically-disadvantaged individuals. We additionally note that the treatment under study (Contingency Management) has been demonstrated to be effective, regardless of income level [71].

View: 6.3 Study Population- Special Populations

Study Population

1.0

* Check all that apply to describe your study population:

Employee and Student Subjects

Investigators Clinical Population

2.0 * Provide a justification for including these subjects:

It is possible that a potentially eligible participant will be a member of a clinical population seen by a study investigator. For example, it is possible that one or more investigators will be involved with administration of CM or other substance use treatment services through the Behavioral Health service line. [name] provided clinical services through the Center for Treatment of Addictive Disorders during active recruitment and the majority of patients who would be eligible for this study will likely be receiving care through this clinic. While subjects from these populations may be at an increased risk of coercion, study procedures have been developed to protect against this risk and are further described under Section 6.3.2. Importantly, patients will regularly be informed/reminded that research is optional and voluntary and that they will have comparable access to Contingency Management treatment if they choose not to participate in the current study.

View: 6.3.2 Investigators clinical population

Investigators clinical population

1.0 * Please indicate how you will minimize the potential for them to feel coerced to participate. Discuss how the potential confusion in roles will be addressed:

It is possible that a potentially eligible participant will be a member of a clinical population seen by a study investigator. For example, it is possible that one or more investigators will be involved with administration of CM or other substance use treatment services through the Behavioral Health service

line. While subjects from these populations may be at an increased risk of coercion, study procedures have been developed to protect against this risk. Specifically, all participants will be asked to provide written informed consent prior to undergoing study procedures and will have the option to voluntarily discontinue the study at any time. During the informed consent process, all participants will be informed of the following: "Your doctor may also be involved as an investigator in this research study. As both your doctor and a research investigator, s/he is interested both in your medical care and the conduct of this research study. You are under no obligation to participate in this or any other research study offered by your doctor. Before you agree to participate in this research study, or at any time during your participation in this study, you may discuss your care with another doctor who is not associated with this research study."

It is noted that some participants will initially receive information about the study from a clinician who is not a study co-investigator and will therefore have an opportunity to discuss participation with this unaffiliated provider. In addition, we anticipate that the majority of potentially eligible participants will self-initiate contact with the study. In such cases, potentially eligible participants would not be under the direct clinical care of a study investigator involved with CM until after they had evaluated their interest in the study and determined whether or not they wished to participate. However, it is possible that participants under direct clinical care by a study investigator could receive information about the study from that investigator in some cases. If this should occur, the investigator will identify that he/she is involved with the study but will arrange that the screening and informed consent process could be conducted by other study personnel if the participant prefers. The investigator will inform potential participants that such arrangements have been made in order to minimize confusion about roles served by the investigator, as well as any perceived pressure to participate. Study personnel will always take care to clearly delineate clinical versus research procedures in which participants may become involved and will make all participants aware that research involvement is voluntary and can be discontinued at any time. Importantly, patients will regularly be informed/reminded that research is optional and voluntary and that they will have comparable access to Contingency Management treatment if they choose not to participate in the current study.

View: 7 Risk/Benefit Assessment-Risks

Risk/Benefit Assessment-Risks

1.0

* Risk classification for this study (select one).

Minimal Risk

Greater than Minimal Risk

2.0 * Basis for making the above recommendation:

The potential risks to subjects in the proposed research are minimal. The proposed work utilizes only noninvasive procedures that suggest a level of risk, comparable to that which is typically encountered in

daily life or in routine physical or psychological examinations or tests. Potential risks include 1) minor itchiness or irritation at EEG electrode sites, 2) distress or discomfort during interview and/or self-report assessments, and 3) loss of confidentiality of information collected in the context of the proposed research. Risks are specific to involvement in proposed research procedures. Participation in this study will not entail any additional therapeutic risk. There are no known contraindications to Contingency Management. Furthermore, patients will be informed that they may withdraw from the study at any time without penalty and will continue to have access to Contingency Management services through CTAD.

3.0 * Describe the safety precautions that will be taken to minimize risks/harms:

Participants will be informed of potential risks during the informed consent procedure and will also be informed of all measures to protect against these risks (detailed below under, Protection Against Risk). The risks associated with the proposed research are minimal and methods in place to protect against these risk have already been evaluated and approved by the VAPHS Institutional Review Board in the context of an ongoing pilot study using procedures described in the proposed research. Consequently, the measures in place to protect against risks in the proposed work are expected to be adequate. The Contingency Management interventions used within this study are already routinely used within the VA and are not associated with any additional risks. Participants will, however, be asked to report any change in substance use, mental health symptoms, or gambling behavior that they notice during Contingency Management; while we have no reason to expect such changes, these symptoms will be monitored in order to guard against unknown risks.

Participants will be informed of potential risks during the informed consent procedure and will also be told that they can discontinue the study at any time without penalty or loss of access to treatment services. Participants will be informed that they do not need to answer questions posed in interviews or on self-report questionnaires if they do not wish to. They will also be asked to report discomfort during the EEG procedure, such as itchiness on the scalp, around electrode sites. If discomfort or distress is reported during any study procedure, the participant will be asked if he/she wishes to discontinue the procedure. Procedures will be discontinued upon participant request at no risk of penalty. As private information will be collected as part of this study, there is a risk of loss of privacy and confidentiality. This risk will be described during the informed consent procedure. In addition, all electronic and paper data will be stored in an approved, secure location and will not be transmitted outside the VA. All possible efforts will be made to limit the inclusion of personally identifiable information on study-related documents. Personal identifiers will not be used to label study data. Participants will be assigned a study ID and this coded number will be used to identify all paper and electronic files related to study participation. The link between the participant ID code and participant name will be maintained in a single file which will be password-protected and accessible by key study personnel only; this file will also be stored behind the VA firewall in a secure location on the VA network. The participant ID code will not be included on informed consent documents or other paper forms that include identifiable information (e.g., contact information) and will be stored separately from documents labeled with a participant ID code. Participants will be informed of information that may be entered in their personal medical record as part of clinical care administered through the study; such information may include urinalysis lab results and Contingency Management progress notes. Participants will also be informed that they can continue with the research study even if they choose to discontinue Contingency Management and/or do not wish to provide urines that will be subject to lab-based urinalysis. It is additionally noted that

